## 7. Changes from Planned Analyses in Protocol

There are no changes from planned analyses in protocol.

## 9. List of Appendices

### 9.1. Appendix A Standards for Safety Variable Display in TFLs

**Continuous Variables:** The precision for continuous variables will be based on the precision of the data itself. The mean and median will be presented to one decimal place more than the original results; the SD will be presented to two decimal places more than the original results; the minimum and maximum will be presented to the same precision as the original results.

**Categorical Variables:** Percentages will be presented to 1 decimal place.

### 9.2. Appendix B Analysis Visit Windows for Safety, Biomarker and Exploratory Analysis

Safety and Biomarker Analysis will be summarized using the following analysis visit window for post-injection assessments:

Step 1: If the safety and biomarker assessments are collected at scheduled visit, i.e., nominal scheduled visit, the data collected at scheduled visit will be used.

Step 2: If the safety and biomarker assessments are not collected at the scheduled visit, assessments collected at unscheduled visit will be used using the analysis visit windows described in [Table 1](#) below.

If a participant has multiple assessments within the same analysis visit, the following rule will be used:

- If multiple assessments occur within a given analysis visit, the assessment closest to the target study day will be used.

If there are 2 or more assessments equal distance to the target study day, the last assessment will be used.

**Table 1 Visit Windows**

Visit	Target Study Day	Visit Window in Study Day	
cTnI (Troponin)			
		Primary Analysis Window [Days, Days]	Additional Analysis Window [Days, Days]
Day 1 (Injection 1)	1 (Pre-Injection)	[Pre-dose actual injection 1]	[Pre-dose actual injection 1]
Day 4	4	[Injection 1 date + 2 days, Injection 1 date + 6 days]	[Injection 1 date + 1 day, Injection 2 date – 1 day]
Day 29 (Injection 2)	29 (Pre-Injection)	[Pre-dose actual injection 2]	[Pre-dose actual injection 2]
Day 32	32	[Injection 2 date + 2 days, Injection 2 date + 6 days]	[Injection 2 date + 1 day, Injection 2 date + 14 days]
Day 57	57	[Injection 2 date + 25 days, Injection 2 date + 31 days]	> Injection 2 date + 14 days
Vital Signs			
Day 1, Pre-Injection	1 (Pre-Injection)	≤1 Pre-Injection	N/A
Day 1, Post-Injection	1 (Post-Injection)	[1 Post-Injection, 1]	N/A
Day 4	4	[2, 17]	N/A
Day 29, Pre-Injection	29 (Date of Collection Pre-Injection)	[18, 29 Pre-Injection]	N/A
Day 29, Post-Injection	29 (Date of Collection Post-Injection)	[29 Post-Injection, 31]	N/A
Day 32	32	[32, 45]	N/A
Day 57	57	≥46	N/A

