### 7.1. Discontinuation of Study Intervention

In rare instances, it may be necessary for a participant to permanently discontinue study intervention. If study intervention is permanently discontinued, the participant should, if at all possible, remain in the study to be evaluated for cTnI levels and safety assessments. See the EOS Visit in the SoA ([Table 1](#)) for data to be collected at the time of discontinuation of study intervention and follow-up and for any further evaluations that need to be completed.

The Investigator, in consultation with the Sponsor's medical monitor, may withhold a participant from study intervention if the participant experiences any of the following prior to injection on Day 1 or Day 29:

- A POCBP becomes pregnant.
- Withdrawal of consent (not related to COVID-19).
- Develops symptoms or conditions listed in the exclusion criteria ([Section 5.2](#)).

The reason(s) for withdrawal from study injection will be recorded in the eCRF.

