### **6.3. Biomarker Analysis**

Biomarker analyses will be based on the Evaluable Set. In an exploratory fashion, the same analyses done on the Evaluable Set will be repeated for the Safety Set as an additional analysis using the windowing described in [Section 9.2](#). The intervention sequences and intervention groups defined in [Section 6.1](#) will both be used for the biomarker analyses.

cTnI will be measured in units pg/mL. Elevated cTnI is defined as per the threshold described in product insert of the high-sensitivity cardiac troponin I (hs-cTnI) assay kit. As this is a blinded study, the results of the hs-cTnI assay will not be available until after the study is completed. Elevated cTnI values will be defined based on the sex-specific 99th percentile cutoff of the assay that will be used for the study, >53.53 in male and >38.64 in female, with units in pg/mL.

Subgroup analyses will be performed according to the following:

- Age (12 through 17 years, and  $\geq$ 18 through 30 years)
- Sex (female, male) at birth
- Race (White, Black or African American, Asian, American Indian or Alaska Native, Native Hawaiian or other Pacific Islander, Other, Unknown, Not Reported). Participants with multiple categories of race or that do not fit under any of the other defined categories will be categorized as Other.
- Ethnicity (Hispanic or Latino, Not Hispanic or Latino, Not Reported, Unknown)

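### In the exploratory Safety Set repeat, the 3-day cTnI window is 27 to 30 days long after Injection 1 but 14 days after Injection 2, and no rule covers a missing Injection 2

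*SAP*

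**What the plan says.** SAP 6.3 bases the biomarker analyses on the Evaluable Set. It adds that, as an exploratory step, "the same analyses done on the Evaluable Set will be repeated for the Safety Set as an additional analysis using the windowing described in" Appendix B (SAP 9.2). Table 1 of that appendix has a primary and an additional window column for cTnI. I take the additional column to be the one meant for the Safety Set repeat, because its heading matches, although 6.3 does not name a column.

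In the additional column:

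- Day 4: "Injection 1 date + 1 day, Injection 2 date – 1 day".
- Day 29: "Pre-dose actual injection 2".
- Day 32: "Injection 2 date + 1 day, Injection 2 date + 14 days".
- Day 57: "> Injection 2 date + 14 days".

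The primary column treats the two injections alike. Its Day 4 window is "Injection 1 date + 2 days, Injection 1 date + 6 days", and Day 32 has the same offsets from Injection 2.

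The steps above the table decide when a window matters. Under Step 1, if there is a scheduled-visit sample, "the data collected at scheduled visit will be used". Under Step 2, the windows place an unscheduled sample when the scheduled one was not collected. If several samples fall in one analysis visit, the one nearest the target day is taken.

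The Safety Set needs only one dose (SAP 5.2). Protocol 7.1 asks that participants who stop study intervention should, where possible, "remain in the study to be evaluated for cTnI levels and safety assessments".

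**The concern.** SAP 6.3.1 reports Day 4 and Day 32 as one visit, 3 days after injection, within each intervention group. Each group draws on both injection periods. A pooled visit should mean the same interval after either injection, and in the additional column it does not. A late sample is called a 3-day value after Injection 1 and a 28-day value after Injection 2.

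The protocol and SAP dismiss carry-over because they expect troponin elevations to clear within days to about two weeks. On that expectation, a sample taken in the third or fourth week says little about the level at 3 days.

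The second gap concerns participants who receive Injection 1 only. They belong to the Safety Set and may still give blood, but the additional column locates every post-injection row by reference to Injection 2. Where their unscheduled samples go would depend on how a program handles a missing date.

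**Working it through.** **The plan's own figure.** Sample size (SAP 4.2): 1000 × (1 − 0.10) = 900 in the mRNA-1273.712 group, true rate 0.3%. The probability of at least one elevation is 1 − (1 − 0.003)^900 = 0.933, which agrees with the stated value of more than 90%. The present point does not depend on it.

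**Window lengths.** The Schedule of Activities puts Injection 2 at Day 29 with an allowance of +3 days, so 28 to 31 days after Injection 1. The Day 4 additional window therefore ends 28 − 1 = 27 to 31 − 1 = 30 days after Injection 1.

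| Additional window | Days after the relevant injection | Length | Furthest from the 3-day target |
|---|---|---|---|
| Day 4 | +1 to +27 (up to +30) | 27 to 30 days | 27 − 3 = 24 to 30 − 3 = 27 days |
| Day 32 | +1 to +14 | 14 days | 14 − 3 = 11 days |

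The stretch treated differently in the two periods starts at +15 days and runs to the day before Injection 2. It is 27 − 14 = 13 to 30 − 14 = 16 days long.

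**One sample followed through.** Suppose the scheduled 3-day sample is missing and one unscheduled sample is taken 20 days after injection.

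- After Injection 1: +20 lies within +1 to +27, so it is filed as Day 4, a 3-day value.
- After Injection 2: +20 exceeds +14, so it falls in the Day 57 window, a 28-day value.

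The nearest-to-target rule does not correct this, because it only chooses among several samples.

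**No Injection 2.** With that date missing, I tested samples at +1, +3, +7, +14, +20 and +27 days after Injection 1. The Day 4 window has no upper limit to compare with, Days 32 and 57 have no starting point, and Day 29 has no dose to precede. None of the six days is placed. The primary Day 4 window (+2 to +6) needs no Injection 2 date and still accepts +3.

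**The same table elsewhere.** The vital-signs rows end Day 4 at study day 17, which is 17 − 1 = 16 days after Injection 1. They end Day 32 at study day 45, which is 45 − 29 = 16 days after an Injection 2 given on Day 29. There the SAP uses the same mid-interval cut after both injections.

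**Size.** The documents do not say how many participants will miss Injection 2. If the 10% all-cause exclusion assumption is taken as a ceiling, the range is 0 to about 100 of 1000. Expected elevations per group of 900 are 900 × 0.003 = 2.7 at the plan's rate. At 1%, an assumed upper value taken from the bound the protocol cites for another mRNA COVID-19 vaccine, they are 900 × 0.01 = 9. The Safety Set may be somewhat larger than 900. One elevated sample filed under the wrong visit would be about 1 in 3 to 1 in 9 of a group's events. That is conditional on such a sample existing and is not an estimate of how often it will.

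**The case against.** The case for leaving this alone is substantial, and much of it stands.

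- The additional column serves an exploratory repeat in a descriptive study with no hypothesis tests. A reader might infer that the primary endpoint result is at risk because the endpoint is Day 4 or Day 32. It is not: the primary analysis uses the Evaluable Set, and the primary windows are symmetric.
- A reader might infer that participants without Injection 2 drop out of the Safety Set repeat. They do not. Step 1 keeps their scheduled Day 4 samples, and only unscheduled samples lack a place.
- A reader might think that a period 1 sample fits both Day 4 and Day 29, since the Day 29 cell gives no earliest day. The natural reading is that the windows adjoin: Day 4 closes the day before Injection 2, and Day 29 is that day's pre-dose sample.
- It is tempting to say that unscheduled samples are symptom-driven and so the likeliest to be elevated. Protocol 8 allows them for safety or for technical reasons, without saying which will dominate. Nothing says that troponins from a clinical work-up enter this dataset.
- Both groups draw on both periods, so no bias toward mRNA-1273.712 or placebo is shown.

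What the objection does not remove is that one pooled visit has two definitions in the same column, and that absence of Injection 2 is not provided for. The Safety Set repeat is where this matters: SAP 5.3 counts missing endpoint assessments among the deviations that can remove a participant from the Evaluable Set. Participants without a scheduled Day 4 sample may therefore appear only in the repeat.

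**Conclusion.** The point holds for the exploratory Safety Set repeat only. The additional Day 4 window is 27 to 30 days long against 14 for Day 32. An unscheduled sample more than 14 days after injection, standing in for a missing scheduled one, is labelled 3-day in period 1 and 28-day in period 2. For participants with Injection 1 only, unscheduled samples have no defined post-injection window.

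The consequence is misclassification in the 3-day estimate, probably of few samples. A bias between groups has not been demonstrated. This rests on two readings: that the additional column is the one SAP 6.3 intends, and that Step 1 takes scheduled samples regardless of the windows. It deserves correction because expected events are few and the table can be repaired before anyone sees which values are affected.

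**What to change.** In the Additional Analysis Window column of SAP Table 1:

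- Day 4: from Injection 1 + 1 day to the earlier of Injection 1 + 14 days and Injection 2 − 1 day.
- Day 29: from Injection 1 + 15 days to the pre-dose sample of Injection 2. If Injection 2 was not given, from Injection 1 + 15 to Injection 1 + 31 days (28 days plus the +3 visit allowance), with later samples listed only.

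Add to Steps 1 and 2 that a sample, scheduled or unscheduled, is summarised as Day 32 or Day 57 only if Injection 2 was given. Step 1 needs this too: Protocol 7.1 directs participants who stop intervention to the end-of-study visit, and their sample could otherwise be reported as 28 days after an injection they never had.

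Day 4 then lasts 14 days, at most 11 days from target, and can be evaluated without an Injection 2 date. A +20-day sample is a 28-day value in both periods. It would also help for SAP 6.3 to name the column.

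The cost is two table cells and a short addition to the steps, made before database lock and unblinding, with no new data. The 14-day cut is itself a convention, and a two-week sample still counts as a 3-day value, but it is the cut the SAP already applies after Injection 2.

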### 9.3. Appendix C Imputation Rules for Missing Prior/Concomitant Medications and Non-Study Vaccinations

Imputation rules for missing or partial medication start/stop dates are defined below:

#### 1. Missing or partially missing medication start date:

If only Day is missing, use the first day of the month, unless the start month and year of the medication coincide with the start month and year of the first IP injection.

- If not marked as a prior medication on the Prior/Concomitant CRF page (“Was the medication taken prior to first study treatment administration?” = “No”), then use the date of the first IP injection.
- If marked as a prior medication on the Prior/Concomitant CRF page (“Was the medication taken prior to first study treatment administration?” = “Yes”), then use the earlier of the first day of the month or the date of the first IP injection.
- If the mark on the Prior/Concomitant CRF page (“Was the medication taken prior to first study treatment administration?”) is missing and the medication end date is on/after the date of the first IP injection or is missing, then use the date of the first IP injection.

If Day and Month are both missing, use the first day of the year, unless the start year of the medication coincide with the start year of the first IP injection.

- If not marked as a prior medication on the Prior/Concomitant CRF page (“Was the medication taken prior to first study treatment administration?” = “No”), then use the date of the first IP injection.
- If marked as a prior medication on the Prior/Concomitant CRF page (“Was the medication taken prior to first study treatment administration?” = “Yes”), then use the earlier of the first day of the year or the date of the first IP injection.
- If the mark on the Prior/Concomitant CRF page (“Was the medication taken prior to first study treatment administration?”) is missing and the medication end date is on/after the date of the first IP injection or is missing, then use the date of the first IP injection.

If Day, Month and Year are all missing, the date will not be imputed, but will use the following rules for purposes of determining the status as prior and/or concomitant.

- If not marked as a prior medication on the Prior/Concomitant CRF page (“Was the medication taken prior to first study treatment administration?” = “No”), then the medication will be treated as having begun after first IP injection.
- If marked as a prior medication on the Prior/Concomitant CRF page (“Was the medication taken prior to first study treatment administration?” = “Yes”), or if the mark is missing, then the medication will be treated as a prior medication (and as a concomitant medication unless the stop date indicates the medication was stopped prior to first IP injection).

2. Missing or partial medication stop date:

If only Day is missing, use the earliest date of (last day of the month, study completion, discontinuation from the study, or death).

If Day and Month are both missing, use the earliest date of (last day of the year, study completion, discontinuation from the study, or death).

If Day, Month and Year are all missing, the date will not be imputed, but the medication will be flagged as a continuing medication.

In summary, the prior, concomitant or post categorization of a medication is described in [Table 2](#) below.

**Table 2 Prior, Concomitant, and Post Categorization of a Medication**

Medication Start Date	Medication Stop Date		
	< First Dose Date of Study Injection	≥ First Dose Date and ≤ End Date of Last Study Injection + 27 days	> 27 Days After Last Injection [2]
< First dose date of study vaccination [1]	P	PC	PCA
≥ First dose date and ≤ 27 days after last injection	-	C	CA
> 27 days after last injection	-	-	A

A: Post; C: Concomitant; P: Prior

[1] includes medications with completely missing start date

[2] includes medications with completely missing end date

#### **9.4. Appendix D Imputation Rules for Missing AE dates**

Imputation rules for missing or partial AE start dates and stop dates are defined below:

1. Missing or partial AE start date:

- If only DAY is missing, use the first day of the month, unless:
  - The AE end date is after the date of first injection or is missing AND the start month and year of the AE coincide with the start month and year of the first injection. In this case, use the date and time of first injection, even if time is collected.
- If DAY and Month are both missing, use the first day of the year, unless:
  - The AE end date is after the date of first injection or is missing AND the start year of the AE coincides with the start year of the first injection. In this case, use the date of first injection.

- If DAY, Month and Year are all missing, the date will not be imputed. However, if the AE end date is prior to the date of first injection, then the AE will be considered a pre-treatment AE. Otherwise, the AE will be considered treatment-emergent.
- 2. Missing or partial AE end dates will not be imputed.

## 9.5. Appendix E Schedule of Assessments

**Table 3: Schedule of Activities**

Visit Number	1	2	3	4	5
Type of Visit	C	C	C	C	C/EOS
Month Timepoint	M0		M1		M2
Timepoint	D1 a (Screening and Baseline)	D4	D29	D32 b	D57 b
Window Allowance (Days)	-7	-2	+3	-2	±3
Days Since Injection	0	3	28/0	3	28
ICF, demographics, concomitant medications, medical history	X				
Confirm participant meets inclusion/exclusion criteria	X				
Full physical examination c	X				
Vital sign measurements d	X	X	X	X	X
Pregnancy testing e	X		X		
Study injection (including 15-minute post-injection observation period) f	X		X		
Blood collection for cardiac troponin I assessment g	X	X	X	X	X
Recording of SAEs, MAAEs, AESIs, AEs leading to withdrawal h	X	X	X	X	X

Visit Number	1	2	3	4	5
Type of Visit	C	C	C	C	C/EOS
Month Timepoint	M0		M1		M2
Timepoint	D1 a (Screening and Baseline)	D4	D29	D32 b	D57 b
Window Allowance (Days)	-7	-2	+3	-2	±3
Recording of concomitant medications	X	X	X	X	X
Recording of nonstudy vaccinations	X	X	X	X	X
Review of eDiary d	X	X	X	X	X
Study completion					X

Abbreviations: AE = adverse event; AESI = adverse event of special interest; C = clinic visit; D = day; eDiary = electronic diary; EOS = end of study; ICF = informed consent form; M = month; MAAE = medically attended adverse event; SAE = serious adverse event.

- a. The Screening Visit and Day 1 (injection/baseline) visit should be performed on the same day. If because of extenuating circumstances, Screening and Day 1 visits need to be performed on 2 different days, completion of Informed Consent Form, demographics, concomitant medications, medical history and confirming participant meets inclusion/exclusion criteria must be completed on the same day (Screening), and the remaining study procedures must be done on the same day as the injection (Day 1).
- b. Visit 4 must be scheduled 3 days after Visit 3 (a window of up to -2 days is permitted). EOS Visit must be scheduled 28 days after Visit 3 (a 3-day window is permitted).
- c. Physical examination: A full physical examination, including height and weight, will be performed on Day 1. Symptom-directed physical examinations may be performed at other timepoints at the discretion of the Investigator.
- d. On the day of injection (Day 1 and Day 29), vital signs are to be collected before and after injection.
- e. Pregnancy tests are to be collected before each injection (Section 8.2.6 in protocol).
- f. For participants who are febrile (body temperature  $\geq 38.0^{\circ}\text{C}$  [ $100.4^{\circ}\text{F}$ ]) before injection on Day 1, the visit must be rescheduled within the relevant window period to receive the injection. Afebrile participants with minor illnesses can be administered study intervention at the discretion of the Investigator. Participants will be encouraged but not required to avoid vigorous physical activities 4 days before and after each injection.
- g. For the blood collection on Day 1 and Day 29, blood will be drawn prior to study injection.
- h. The study site also has the discretion to make safety telephone calls or send text messages to remind the participant about visits or follow up with ongoing or outstanding issues.
- i. Concomitant medications (associated with SAEs, MAAEs, AESIs, or AEs leading to withdrawal) and non-study vaccinations will be recorded through the EOS.
- j. Study site staff will review eDiary data with participants at each clinic visit after the first injection.

**Table 4: Schedule of eDiary Collection of Vigorous Physical Exercise**

Visit Number	1				2				3				4				5
Description	4 days post-Injection #1				4 days pre-Injection #2				4 days post-Injection #2				4 days pre-EOS				EOS b
Day a	1	2	3	4	25	26	27	28	29	30	31	32	53	54	55	56	57

Abbreviations: eDiary = electronic diary; EOS = end of study.

a. Window Allowance (Days) for the study injections and EOS are presented in Schedule of Activities ([Table 3](#)). Depending on when the study injections or EOS is completed, the participant must complete the eDiary for: 4 consecutive days post-Injection 1, 4 consecutive days pre- and post-Injection 2, 4 consecutive days prior to EOS visit, and on the day of the EOS visit.

b. eDiary entry will be logged at clinic visit on Day 57.

## 9.6. Appendix F Vital Signs Toxicity Grading Scale for Healthy Adult and Adolescent Volunteers Enrolled in Preventive Vaccine Clinical Trials Appendix E Schedule of Assessments

**Table 5: Severity Grading of Vital Sign Abnormalities**

Vital Signs *	Mild (Grade 1)	Moderate (Grade 2)	Severe (Grade 3)	Potentially Life Threatening (Grade 4)
Fever (°C) ** (°F) **	38.0 – 38.4 100.4 – 101.1	38.5 – 38.9 101.2 – 102.0	39.0 – 40 102.1 – 104	> 40 > 104
Tachycardia - beats per minute	101 – 115	116 – 130	> 130	ER visit or hospitalization for arrhythmia
Bradycardia - beats per minute***	50 – 54	45 – 49	< 45	ER visit or hospitalization for arrhythmia
Hypertension (systolic) - mm Hg	141 – 150	151 – 155	> 155	ER visit or hospitalization for malignant hypertension
Hypertension (diastolic) - mm Hg	91 – 95	96 – 100	> 100	ER visit or hospitalization for malignant hypertension
Hypotension (systolic) – mm Hg	85 – 89	80 – 84	< 80	ER visit or hospitalization for hypotensive shock
Respiratory Rate – breaths per minute	17 – 20	21 – 25	> 25	Intubation

\* Participant should be at rest for all vital sign measurements.

\*\* Oral temperature; no recent hot or cold beverages or smoking.

\*\*\* When resting heart rate is between 60 – 100 beats per minute. Use clinical judgement when characterizing bradycardia among some healthy participant populations, for example, conditioned athletes.

